# 7.1.4. Hyperpolarized He Contrast

For imaging, a gas contrast agent is used - hyperpolarized  $^3$ He gas. The helium component of a 99.25% Medical grade  $^3$ He; 0.75% Medical grade  $N_2$  mixture is polarized using a GE polarizer IGI.9600, until approximately 30% of the Helium is polarized. 5mL/kg (participant body weight) of this gas is mixed with Medical Grade  $N_2$  to form a 1L volume and is dispensed immediately to the participant through a sample bag and straw while the participant is supine in the scanner.  $^3$ He gas has been used in previous human studies at 0.5T, 1.5T and 3T with excellent safety and tolerability reported.

# 7.1.5. fMRI BOLD Contrast Signal and DTI

For brain imaging, BOLD contrast will be used to measure physiological changes in blood flow and oxygen metabolism in the brain. The magnetic properties of oxygen-rich and oxygen-deficient blood provide a MR signal to indicate underlying neural activity changes.

DTI will be utilized to analyze and track neural pathways. The magnetic resonance signal is able to track the random motion of water molecules in white matter fiber tracts. The diffusion along the fibers provides information of the magnitude, orientation, and direction of cerebral connections.

DATE: November 15, 2024

# 7.2. Safety Parameters

# 7.2.1. General Safety

Adverse events (AEs) may occur in the course of the study within the screening or the follow-up period of 24 hr. Although there is no investigational drug or vaccine being administered, participants will be followed for all procedure-related serious adverse event (SAE) for 24 hours following each visit. Such events will be recorded at each examination in the study file.

Such events will be recorded at each examination on the AE Case Report Forms. An AE is defined as any unfavorable and unintended change in the structure, function, or chemistry of the body temporally associated with the test procedure, whether or not considered related to the test procedure. Any worsening (i.e., any clinically significant adverse change in frequency and/or intensity) of a pre-existing condition which is temporally associated with the test procedure, is also an AE.

An investigator, who is a qualified physician, will evaluate all AEs as to:

# Maximum intensity:

- Mild (awareness of sign or symptom, but easily tolerated);
- Moderate (discomfort enough to cause interference with usual activity);
- Severe (incapacitating with inability to work or do usual activity).

#### Seriousness:

An SAE is any AE that:

†Results in death; or

†Is life threatening (places the participant, in the view of the investigator, at immediate risk of death from the event as it occurred [Note: This does not include an AE that, had it occurred in a more severe form, might have caused death.]); or

†Results in a persistent or significant disability/incapacity (substantial disruption of one's ability to conduct normal life functions); or

†Results in or prolongs an existing inpatient hospitalization (hospitalization is defined as an inpatient admission, regardless of length of stay, even if the hospitalization is a precautionary measure for continued observation) (Note: hospitalization [including hospitalization for an elective procedure] for a pre-existing condition which has not worsened does not constitute am SAE.); or

†Is a congenital anomaly/birth defect (in offspring of participant taking the product regardless of time to diagnosis); or

Is a cancer; or

Is an overdose (whether accidental or intentional).

Other important medical events that may not result in death, not be life threatening, or not require hospitalization may be considered a SAE when, based upon appropriate medical judgment, the event may require medical or surgical intervention to prevent one of the outcomes listed previously (designated above by a †).

#### Duration:

DATE: November 15, 2024

Record the start and stop dates of the AE. If less than 1 day, indicate the appropriate length of time and units.

#### Action taken:

Did the AE cause the test procedure to be discontinued?

#### Relationship to test procedure:

The determination of the likelihood that the test procedure caused the AE will be provided by an investigator who is a qualified physician. The investigator's signed/dated initials on the source document or case report form, supporting the causality noted on the AE form, ensures that a medically qualified assessment of causality was done. This initialed document must be retained for the required regulatory time frame. The criteria below are intended as reference guidelines to assist the investigator in assessing the likelihood of a relationship between the test procedure and the AE based upon the available information.

The following components are to be used to assess this relationship; the greater the correlation with the components and their respective elements (in number and/or intensity), the more likely the test procedure caused the AE:

#### Exposure:

o Is there evidence there was an actual exposure to the test procedure?

#### Time Course:

- Did the AE follow in a reasonable temporal sequence from administration of the test procedure?
- o Is the time of onset of the AE compatible with a procedure-induced effect?

#### Likely Cause:

 Is the AE not reasonably explained by another etiology such as underlying disease, other procedure(s), or other host or environmental factors?

The assessment of relationship will be reported on the case report forms by an investigator who is a qualified physician according to his/her best clinical judgment, including consideration of the above elements. Use the following scale of criteria as quidance (not all criteria must be present to be indicative of a procedure relationship).

#### • Definitely related to test procedure:

- There is evidence of exposure to the test procedure.
- The temporal sequence of the AE onset relative to administration of the test procedure is reasonable.
- The AE is more likely explained by the test procedure than by another cause.
- The AE shows a pattern consistent with previous knowledge of the test procedure.

#### Probably related to test procedure:

- There is evidence of exposure to the test procedure.
- The temporal sequence of the AE onset relative to administration of the test procedure is reasonable.
- The AE is more likely explained by the test procedure than by another cause.

- Possibly related to test procedure:
  - There is evidence of exposure to the test procedure.
  - The temporal sequence of the AE onset relative to administration of the test procedure is reasonable.
  - The AE could have been due to another equally likely cause.
- Probably not related to test procedure:
  - There is evidence of exposure to the test procedure.
  - There is another more likely cause of the AE.
- Definitely not related to test procedure:
  - Did not receive the test procedure.

OR

 Temporal sequence of the AE onset relative to administration of the test procedure is not reasonable.

OR

There is another obvious cause of the AE.

Any SAE, including death, related to the procedure, from the time the consent is signed through 24 hours thereafter, will be reported within 24 hours to the PI and UWO Health Sciences Research Ethics Board. All AEs will be assessed and evaluated 24 hours after study completion.

# 7.2.2. Immediately Reportable AEs

ANY CLINICAL AE OR ABNORMAL LABORATORY TEST VALUE THAT IS **SERIOUS** (INCLUDING DEATH, OVERDOSE OR CONGENITAL ANOMALY) OCCURRING DURING THE COURSE OF THE STUDY, IRRESPECTIVE OF THE TREATMENT RECEIVED BY THE PARTICIPANT, MUST BE REPORTED WITHIN **ONE** WORKING DAY OF OCCURRENCE.

An SAE is any experience that suggests a significant hazard, contraindication, side effect or precaution. With respect to human clinical experience, this includes any experience which

- is fatal or life-threatening;
- is permanently disabling, i.e., incapacitating or interfering with the ability to resume usual life patterns;
- requires in-patient hospitalization or prolongation of hospitalization;
- is a congenital anomaly, cancer; or
- is an overdose.

The term **severe** is a measure of **intensity**: thus, an SAE is not necessarily **serious**. For example, nausea of several hours' duration may be rated as severe, but may not be clinically serious.

An **overdose** is a deliberate or inadvertent administration of a treatment at a dose higher than that specified in the protocol and higher than known therapeutic doses. It must be reported irrespective of outcome even if toxic effects were not observed.

DATE: November 15, 2024

A **death** occurring during the study or which comes to the attention of the investigator within 4 weeks after stopping the treatment whether considered treatment-related or not, must be reported.

For all AEs, the following must be assessed and recorded on the AEs page of the Case Report Form: intensity, relationship to test substance, action taken regarding test substance, and outcome to date.

Such preliminary reports will be followed by detailed descriptions later, which will include copies of hospital case reports, autopsy reports and other documents when requested and applicable.

The Health Sciences Research Ethics Board at The University of Western Ontario will be notified of such an event in writing as soon as is practical.

SAEs related to the 129Xe Radio Frequency Coil for Human Lung Imaging, CMRS Flexible Lung Coil and/or 129Xe Lung Coil devices:

The qualified investigator is required to report SAEs to Health Canada and to the manufacturer and importer within 72 hours of discovery in cases in which the incident is related to failure of the device or a deterioration in its effectiveness, or an inadequacy in its labelling or in its directions for use and has led to the death or a serious deterioration in the state of health of a patient, user or other person, or could do so were it to recur.

Manufacturers and importers are required to provide a preliminary and a final report in respect of the incident within 10 days after they become aware of the incident, if 1) the incident has led to the death or a serious deterioration in the state of health of a patient, user or other person or 2) within 30 days after they become aware of the incident if the incident has not led to the death or a serious deterioration in the state of health of a patient, user or other person, but could do so were it to recur.

#### 7.2.3. Premature Withdrawal/Discontinuation Criteria

Participants will be discontinued from further study participation if:

- A clinical AE occurs suggesting that:
  - The participant's health may be in jeopardy from continued participation in the study;

OR

- The participant is unable to complete the study procedures successfully for any reason
- Participant discloses they are pregnant.
- The participant withdraws from the study at any time.

Any AEs, present at the time of discontinuation/withdrawal, should be documented and followed until resolution.

#### 8. IMAGE ANALYSIS AND STATISTICAL ANALYSIS PLAN

All images will be analyzed in a dedicated image visualization environment with room lighting levels equivalently established for all image analysis sessions.

1) Apparent Diffusion Coefficient (ADC) measurements and ADC maps During a single breath-hold, two interleaved images are acquired – one without diffusion sensitization and the second image acquired with the presence of diffusion sensitization DATE: November 15, 2024

through the application of the additional pulsed magnetic field gradient with pulse duration  $\delta$  and maximum value  $\mathbf{g}$ . The signal intensity of the second image is derived from

$$S = S_0 \exp(-b \cdot ADC)$$

where  $\mathbf{S_0}$  is a signal intensity of the first image, ADC is an apparent self-diffusion

coefficient and  $\mathbf{b} = \frac{2}{3}\gamma^2\delta^3\mathbf{g}^2$  ( $\gamma$  is a gyromagnetic ratio). Accordingly, the **ADC** value

for each image pixel on a pixel by pixel basis or location can be calculated from the following equation:

$$\text{ADC} = \frac{ln\!\!\left(\frac{S_0}{S}\right)}{b}$$

Diffusion weighted images from each visit will be reviewed and compared with the H anatomical images. Mean, whole lung, and centre slice ADC (and standard deviation) will be calculated from the maps based on the formula above and recorded. ADC values will also be calculated for each slice and for six regions of interest to assess regional variation in this measure. ADC gradients in the superior-inferior and anterior-posterior directions will be calculated for each participant and visit.

2) Ventilation Defect Percent (VDP) and H MRI thoracic cavity volume (TCV) Ventilation defect volume (VDV), VDP, ventilation volume (VV) and percent ventilated volume (PVV) will be generated for whole lung and individual lung slices using manual or semi-automated segmentation. For H thoracic cavity images, the TCV will be calculated by manual or semi-automated segmentation [29,30].

3) Xe Dissolved phase spectroscopy measurements

Xe dissolved phase MRI data will be reconstructed using a re-gridding method. The following ratios will be determined by the area-under-the curve obtained from spectroscopy: red-blood-cell to alveolar membrane ratio (RBC:membrane); RBC to gas ratio (RBC:gas); and the membrane to gas ratio (membrane:gas). Spectroscopic signals will be used to reconstruct perfusion and alveolar membrane maps.

Seven-day, 14-day and 1-year reproducibility of Xe MRI measurements will be determined using the coefficient of variation and intraclass correlation coefficients (ICC). The changes in regional VDP will be evaluated for all participants after 2 years pre- and post-salbutamol.

We will evaluate Pearson correlations for MRI measurements (VDP, TCV) with CT (WA%), spirometry and plethysmography measurements to determine whether structure relates to function (and *vice versa*). We will also evaluate the relationship between sputum, biopsy, CT and MRI measurements. Significant differences in Pearson correlations will be determined using 95% Confidence Intervals (CI). To evaluate agreement between measurements, Bland-Altman plots will be generated to show the differences between WA% and He VDP with Xe VDP.

Univariate and multivariate regression models will also be used and adjusted for confounders to assess correlations of imaging measurements with dyspnea score, and asthma control measures for a better understanding of the relationship between imaging and established/validated clinical measurements of asthma. We will also examine the relationship between clinically defined asthma severity and imaging. In each of these models, we will employ a forward stepwise selection modeling process to maximize the

DATE: November 15, 2024

efficiency, while maintaining the validity of the modeling process. We will select only those covariates with a p-value of 0.25 or less and include only those variables that have a p-value of 0.2 or less in the final model. From these models, we will determine the total  $R^2$  values as well as partial  $R^2$ . The Holm-Bonferroni correction will adjust for multiple comparisons.

For participants undergoing fMRI, we will utilize an unpaired two tailed t-test to assess the differences of BOLD and DTI signal intensity between asthma underperceivers and healthy controls. Furthermore, we will assess Pearson correlations for fMRI measurements (BOLD signals and DTI data) with lung MRI and spirometry measurements. Spearman correlations will be used to analyze the relationship between fMRI measurements and Asthma Control Questionnaire (ACQ) scores. Significant differences in Pearson and Spearman correlations will be determined using 95% CI.

For healthy volunteers and asthmatic underperceivers undergoing fMRI, we will utilize a paired two tailed t-test to assess the within group differences of BOLD and DTI signal intensity before and after a methacholine challenge. Pearson correlations will be used to assess the relationship between quantitative fMRI data and spirometry measurements. Significant differences in Pearson correlations will be determined using 95% CI.

To demonstrate if differences exist in BOLD and DTI signal between asthmatics and healthy volunteers post methacholine challenge, we will utilize an unpaired two tailed t-test. Pearson correlations will be used to assess the relationship between quantitative fMRI data and spirometry measurements. Significant differences in Pearson correlations will be determined using 95% CI.

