		Questionnaire.				
DOSAGES		There is no study medication evaluated. As part of the lung MRI, participants will inhale polarized  Xe and/or  He at a dosage of 5 ml/kg body weight diluted with helium-4 (  He) gas to 1.0L. The polarized  Xe/  He mixture will be inhaled in a single breath-hold. This is intended to fill the lungs with the gas, allowing for complete imaging. Participants will inhale the gas mixture up to five times at each imaging session.				
ROUTE OF ADMINI	STRATION	Oral inhalation directly into lungs from a Tedlar ® plastic bag with an attached breathing tube/straw containing a stopcock on-off valve while inside MR magnet bore.				
MAIN PARAMETER -SAFETY	S OF:	Heart rate and oxygen saturation will be monitored throughout the imaging session and recorded. Adverse events will be recorded.				
-EFFICACY		
 
129Xe MRI ventilation image analysis (VDP)
 
129Xe MRI diffusion-weighted image analysis (ADC)
 
129Xe MRI dissolved phase spectroscopy analysis
 
Pulmonary Function Testing
 
MDCT image analysis
 
				
DURATION OF STU	IDY	Q1 2013 - Q4 2028				

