#### **DURATION OF THE STUDY:**

Study duration for each participant is up to 10 years (up to 10 face-to-face visits, 2 phone calls). A sub-set will also visit at 7  $\pm 2$  days and 14  $\pm 2$  days to evaluate reproducibility and for generation of temporal spatial maps. Each participant will spend approximately 1 ½ to 2 hours on site for each visit, including screening, full pulmonary function tests and MRI. There is a 24-hour follow up for adverse events after the end of the final visit.

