#### 4. EXPERIMENTAL DESIGN AND METHODS

# 4.1. Overall Design and Control Methods

In 200 asthma patients, we propose to apply Xe MR image acquisition and analysis methods in order to characterize and probe the relationship between lung structure and function using imaging.

The first 60 participants with asthma will also be asked to complete additional follow up visits at the clinic after 2, 4 and 78 weeks. These visits are detailed in the schedule below.

The 30 healthy volunteers will be asked to complete the same study procedures to allow for a comparison between the resting state brain activity as well as lung structure and function between those with and without asthma.

All participants will visit Robarts Research Institute according to the following schedule:

V1 Baseline	V1a* BL+14±2d	V1b* BL+28±2d	V2 Telephone/ optional In-person BL+52±2wk	V1c* BL+78±8wk	V3 Telephone/ optional In-person BL+104±8wk	V4-10 optional in- person annual visit
 Xe/  He MRI	 Xe/  He MRI	 Xe/  He MRI	 Xe/  He MRI	 Xe/  He MRI	 Xe/  He MRI	 Xe/  He MRI
Full PFT	Full PFT	Full PFT	Full PFT	Full PFT	Full PFT	Full PFT
MCh	Meds/Exac	Meds/Exac	Meds/Exac	Meds/Exac	Meds/Exac	Meds/Exac
FOT	FOT	FOT	FOT	FOT	FOT	FOT
FeNO	FeNO	FeNO	FeNO	FeNO	FeNO	FeNO
BORG	BORG	BORG	BORG	BORG	BORG	BORG
MRC	MRC	MRC	MRC	MRC	MRC	MRC
sputum			sputum	sputum	sputum	sputum
СТ						
RS-fMRI (if applicable)						

\*Applicable to only the first 60 participants with asthma.

DATE: November 15, 2024

All participants with asthma will also complete bi-weekly and weekly quality of life questionnaires. Self-reported data will be uploaded by each participant monthly to our website using a confidential and password protected upload.

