#### 5.1. Inclusion Criteria

- Participants male and female aged 18-85 with a clinical diagnosis of asthma
- Healthy participants male and female aged 18-85
- Asthmatic participants with smoking history ≤ 1 pack/year
- Participant understands the study procedures and is willing to participate in the study as indicated by signature on the informed consent
- Participant is judged to be in otherwise stable health on the basis of medical history
- Participant able to perform reproducible pulmonary function testing (i.e., the 3 best acceptable spirograms have FEV1 forced vital capacity (FVC) values that do not vary more than 5% of the largest value or more than 100 ml, whichever is greater.)
- FEV1 >60% predicted

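### Section 8 reports VDP reproducibility only as a CV and an ICC, so scan-rescan error in VDP percentage points is never stated, and the CV is unstable or undefined at or near zero.

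*Protocol*

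**What the plan says.** Section 8 sets three reproducibility intervals ("Seven-day, 14-day and 1-year reproducibility of" the xenon scans) and two statistics: "MRI measurements will be determined using the coefficient of variation and intraclass correlation coefficients (ICC"). It gives no formula for the CV, no form of the ICC and no rule for zero values.

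The sentence does not name VDP, but the synopsis heads its efficacy list with "129Xe MRI ventilation image analysis (VDP"). Section 8 also states that "VDP, ventilation volume (VV) and percent ventilated volume (PVV) will be generated for whole lung and individual lung slices".

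The extra early visits in the Section 4.1 schedule carry the note "Applicable to only the first 60 participants with asthma". The synopsis, under duration of the study, gives the purpose of its short-interval visits as "to evaluate reproducibility and for generation of temporal spatial maps". Entry requires "FEV1 >60% predicted" (Section 5.1).

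Bland-Altman plots appear in Section 8 only for comparing different measures (CT wall area percent, helium VDP, xenon VDP), not for repeat scans of the same measure.

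Two parts of the protocol depend on VDP change within a participant. The first hypothesis in Section 3 has annual VDP worsening, or improving with therapy, over a decade. Section 8 evaluates regional VDP change after 2 years.

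**The concern.** A CV divides the within-participant SD by the mean. For a quantity that can reach zero, the denominator can become very small or vanish. A slice or lung that reads 0% on every scan has no CV at all. Above zero, a scanner with one fixed level of noise gives a large CV in mild disease and a small one in severe disease.

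The ICC has no difficulty at zero, but it is a ratio of between-participant variance to total variance. It rises when participants differ more, even if the scan is no better.

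Both statistics are free of units. Someone who later sees a participant's VDP move by a few points needs to know how many points two scans can differ through noise alone. The planned summary would not state that.

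**Working it through.** **Inputs.** The protocol gives no VDP mean, spread or scan-rescan error and no reproducibility figure, so there is nothing to reproduce. All VDP values below are assumptions.

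**Formulas.** With within-participant SD σw and between-participant SD σb:
- CV = σw / mean
- ICC = σb² / (σb² + σw²)
- Repeatability coefficient (RC) = 2.77 × σw, in VDP points (2.77 = 1.96 × √2)

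**Step 1: direct arithmetic.** With σw = 1 point, CV = 1/mean: 100% at VDP 1%, 50% at 2%, 20% at 5%, 10% at 10% and 5% at 20%.

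**Step 2: simulation, constant error.** 200,000 participants with 3 scans each, log-normal true VDP (log-SD 0.8), normal scan error, readings cut off at 0. Mean of individual CVs:

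| Median VDP | 2% | 4% | 8% | 12% |
|---|---|---|---|---|
| Mean CV, error 1 point | 52% | 30% | 15% | 10% |
| Estimated σw, error 1 point | 0.94 | 0.98 | 1.00 | 1.00 |
| Mean CV, error 2 points | 78% | 52% | 30% | 20% |

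The estimated σw in the second row only returns the assumed input, slightly reduced at low VDP by the cut-off at 0. The result to note is how far the CV moves while the error stays the same.

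**Step 3: can CV and ICC together recover the error?** Multiply every VDP value by a constant c. Then σw, σb and the mean all multiply by c, and CV and ICC do not change. In the simulation:

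| Case | Mean CV | ICC | σw | RC |
|---|---|---|---|---|
| Median 2%, error 1 point | 52% | 0.88 | 0.94 | 2.6 points |
| Median 4%, error 2 points | 52% | 0.88 | 1.88 | 5.2 points |

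The second case has twice the noise, and both planned statistics are the same.

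**Step 4: ICC and spread.** In a second simulation (60 participants, 3 scans, gamma-distributed VDP, 400 runs) with error 1 point, the ICC runs from 0.72 to 1.00 as between-participant SD rises from 1.6 to 16 points. With that SD held at 4 points, the ICC is 0.94 at mean VDP 5, 10 and 20%. It follows spread, not the mean.

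**Step 5: undefined values.** In the second simulation at mean VDP 2% and error 1 point, about 1% of participants read 0 on all three scans and have no CV. Slice-level VDP was not simulated.

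**Step 6: the opposite error pattern.** With error equal to 20% of true VDP, the mean individual CV in the second simulation is about 18% at every mean from 2 to 20%. The within-participant SD then runs from 0.5 points at mean 2% to 5.0 points at mean 20%, so a single RC in points would be the figure that depends on severity.

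**The case against.** **The CV does carry repeatability.** In the second simulation at mean VDP 10%, doubling the error from 1 to 2 points moves the pooled CV from 10% to 20%. A reader might infer that the CV shows only how mild the sample is. That goes too far: it reflects both error and severity, and if error is proportional to VDP it is the better summary. The protocol does not say which pattern holds. Strict proportionality would mean no error at all at zero, but that does not settle the pattern over the rest of the range.

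**Near-zero values are possible, not shown.** A reader might take the FEV1 entry limit as proof that VDP will be low. Section 1 itself argues that FEV1 can miss peripheral airway dysfunction, and the dedicated repeat visits are for asthma participants only. The zero problem is most plausible for single slices.

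**The CV does not stand alone.** The same sentence plans the ICC, which is unaffected by zeros. This stands, but Steps 3 and 4 show that it does not supply the missing quantity.

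**ADC gradients.** Section 8 says "ADC gradients in the superior-inferior and anterior-posterior directions will be calculated for each participant and visit". These are signed, so a CV would be meaningless around zero. A reader might infer that such a CV is planned, but Section 8 does not say so. It is only one reading of a general sentence. Whole-lung ADC, VV and PVV do not raise the near-zero problem.

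**This is exploratory work and partly SAP detail.** The protocol sets no threshold for individual change, and the form of the CV and the treatment of zeros may be in a SAP that is not shown. The within-participant SD is also the numerator of the CV, so it will be computed anyway. All of this lowers the weight of the point. Even so, Section 8 does name its statistics, and neither is in VDP points.

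**Conclusion.** The point holds in a limited form. Followed as written, Section 8 summarises VDP repeatability with two unit-free statistics. One mixes error with severity and can be undefined at zero, and the other depends on between-participant spread. From those two alone the error in percentage points cannot be recovered, and this follows from the formulas without any assumption about VDP.

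The size does rest on assumptions. With constant 1-point error, mean CV falls from about 52% at median VDP 2% to about 10% at median 12%. With proportional error, the CV is constant and the absolute SD changes. The documents do not support saying that the CV is uninformative, that this sample will sit near zero, or that the CV should be removed. The change is worth making because later VDP changes within participants cannot be weighed against scan noise without it.

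**What to change.** In Section 8, for VDP (whole lung and slice):

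- Add the within-participant SD and the repeatability coefficient (2.77 × SD), in percentage points, from the short-interval repeat scans.
- Add test-retest Bland-Altman limits.
- Plot SD against mean, and use a transformed scale if SD rises with the mean.
- Keep the ICC with its 95% CI.
- Keep the CV for VDP as descriptive only, and state how zero values are handled.

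Apply the same to ADC gradients if their reproducibility is reported. The CV can stay for measures far from zero, such as TCV.

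The new text also has to name the repeat scans it uses. The synopsis and Section 8 refer to 7 and 14 days, while the Section 4.1 schedule places the early repeat visits at 14 and 28 days. These passages must be reconciled.

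The cost is a little more analysis work and revised wording, with no new data and no added burden on participants.

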#### 2. OBJECTIVES OF STUDY

- Acquire Xe MRI and optimize analysis methods to generate *in vivo* measurements
- Evaluate Xe MRI measurements over time and in response to therapy, relate them to airflow, dyspnea, airway remodeling and inflammation and validate using x-ray computed tomography (CT) and histology
- Evaluate image analysis methods that generate Xe MRI temporal lung function maps as image guidance/therapy planning tools for targeted asthma therapy
- Develop Xe MRI structure-function models computationally to understand mechanisms of localized therapy response
- Evaluate oscillometry outcomes of the respiratory system as they correlate to lung function abnormalities detected using Xe MRI
- For the subset of patients identified as underperceivers using asthma control and quality of life questionnaires, we will acquire fMRI to determine if severe asthmatics with poor control exhibit baseline differences in brain structure and function compared to healthy volunteers, and if these alterations influence asthma symptom perception.
- To determine if differences in brain structure and function are related to lung function abnormalities quantified by pulmonary MRI
- In healthy volunteers and the subset of asthmatic participants identified as underperceivers, to determine if differences exist in resting state brain connectivity pre- and post-Methacholine challenge
- In the subset of asthmatic participants, to evaluate the differences in resting state brain connectivity compared to healthy volunteers post-Methacholine Challenge

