# 4.1.6. Multi-Detector Computed Tomography (MDCT)

Thoracic low dose MDCT will be performed with the same inhalation breath-hold volume and maneuver ( $N_2$  gas only) used for MRI to obtain participant-specific high resolution images of lung anatomy (tissue structure and airway morphology). CT imaging will be performed using an Aquilion ONE CT scanner (Canon Medical Systems USA, INC., Tustin, CA, USA) or a Lightspeed VCT CT scanner (General Electric, Waukesha WI, USA) at either Robarts Research Institute in London, Ontario or at University Hospital, located next door to Robarts Research Institute. Participants will be scanned in the supine position and during inspiration breath-hold after inhaling 1L of  $N_2$  in order to match CT and MRI breath-hold volumes and anatomy.

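### Section 8 plans a Bland-Altman agreement analysis of CT WA% against MRI VDP, which are different quantities, so the bias and limits for that pair cannot be read as agreement

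*Protocol*

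**What the plan says.** The statistical paragraphs of Section 8 (Image Analysis and Statistical Analysis Plan) contain two relevant sentences.

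The first is about association: "Pearson correlations for MRI measurements (VDP, TCV) with CT (WA%), spirometry and plethysmography measurements to determine whether structure relates to function". WA% is labelled there as a CT measurement and stands on the structure side. Confidence intervals of 95% are specified for the correlations.

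The second is about agreement: "Bland-Altman plots will be generated to show the differences between WA"%, followed by 3He VDP, compared with 129Xe VDP. The wording is loose. It may mean WA% against 129Xe VDP and 3He VDP against 129Xe VDP, or WA% against 3He VDP with 129Xe VDP alongside. On either reading WA% is differenced with a VDP.

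Three other places say what the quantities are and what they are for:

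- Section 8, item 2, derives VDP from segmented ventilation images: "Ventilation defect volume (VDV), VDP, ventilation volume (VV) and percent ventilated volume (PVV) will be generated for whole lung".
- Section 4.1.6 says that CT is acquired to give "high resolution images of lung anatomy (tissue structure and airway morphology").
- The second objective in Section 2 is to relate 129Xe MRI to clinical and inflammatory measures and to "validate using x-ray computed tomography (CT) and histology". The second hypothesis in Section 3 expects ventilation abnormalities to be related to airway morphology. It does not expect the two to be equal.

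**The concern.** A Bland-Altman plot asks whether one method could replace another. The bias estimates systematic error between the methods, and the limits show how far apart two readings on one person are likely to be. Both presuppose that, with perfect measurement, the two values would be equal.

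Nothing in the protocol suggests that WA% and VDP would be equal. Both carry a percent sign, but one describes airway structure on CT and the other the share of lung that is a ventilation defect on MRI. Their difference estimates no error of either method.

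At stake is the reporting of the CT validation in the second objective. This is the only analysis of the CT-MRI pair that the plan labels as agreement. A large bias, wide limits or a steep trend could be reported as 129Xe MRI failing against CT, when the plot shows only that two scales differ.

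**Working it through.** The plan gives no figure to reproduce, and no mean or SD for WA% or VDP. All numerical inputs below are therefore assumptions, used only to show how the plot behaves.

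**Formulas.** Let WA% have mean m1 and SD s1, VDP have mean m2 and SD s2, and let r be their correlation.

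- Bias = m1 - m2. The correlation r does not enter.
- Half-width of the limits = 1.96 × √(s1² + s2² - 2·r·s1·s2).
- Correlation of the difference with the mean = (s1² - s2²) / √[(s1² + s2²)² - 4·r²·s1²·s2²].

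**Trend and limits, with assumed s1 = 3 and s2 = 6 points.** Here s1² + s2² = 45, 2·s1·s2 = 36, s1² - s2² = -27 and 4·s1²·s2² = 1296.

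| r | Half-width of limits | Difference-mean correlation |
|---|---|---|
| 0 | 1.96 × √45 = 13.1 | -27/√2025 = -0.60 |
| 0.3 | 1.96 × √34.2 = 11.5 | -27/√1908.4 = -0.62 |
| 0.6 | 1.96 × √23.4 = 9.5 | -27/√1558.4 = -0.68 |
| 0.9 | 1.96 × √12.6 = 7.0 | -27/√975.2 = -0.86 |
| 1.0 | 1.96 × √9 = 5.9 | -27/√729 = -1.00 |

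As the relation strengthens, the limits narrow but the trend steepens. At r = 1 every point lies on a sloping line, because VDP then moves exactly 2 points for each point of WA%. A reader looking for agreement would call that strong proportional bias. If the SDs were reversed, the sign of the trend would flip. If they were equal, the trend would vanish.

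**Bias, with assumed means.** Taking mean WA% as 50 to 70 and mean VDP as 3 to 20, the bias runs from 50 - 20 = 30 to 70 - 3 = 67 points, at any r. Two cases:

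- WA% 60 (SD 4) and VDP 10 (SD 8): bias 50. The limits are 32.5 to 67.5 at r = 0 and 42.2 to 57.8 at r = 1.
- WA% 50 (SD 3) and VDP 3 (SD 3) with r = 1: bias 47, and both limits are also 47. The relation is perfect and the measures share one SD, yet the plot reports a 47-point disagreement.

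**Same check for 3He VDP versus 129Xe VDP.** Both are ventilation defect percent, obtained with two gases. Equality is the natural expectation, so bias and limits mean what the method says they mean.

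**The case against.** The strongest reply is that little depends on this plot. The synopsis calls the study exploratory. The sentence attaches no margin, test or decision rule to the plot, and no hypothesis in Section 3 rests on agreement between WA% and VDP. The analysis that suits the pair, a Pearson correlation with a 95% CI, is already planned in the same paragraph, together with an evaluation of how sputum, biopsy, CT and MRI measurements relate. All of this stands. It limits the consequence and sets the severity, but it does not make the planned comparison interpretable.

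A reader might infer more than the protocol supports, in four ways:

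- That the CT validation in the second objective fails. It does not, because the planned correlations address it without this plot.
- That the plot hardly changes with the strength of the relation. That is roughly true of the trend at low r, but the limits more than halve between r = 0 and r = 1.
- That WA% and VDP are unrelated. The protocol hypothesises a relation. They are different quantities, which is all the argument needs.
- That the plot might be taken as successful validation. A large bias and a steep trend offer no plausible route to that reading.

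The protocol does not expand the abbreviation WA%. Its label as a CT measure, and its place on the structure side of the structure-function question, are enough here.

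**Conclusion.** The point holds for the WA% comparison only, on either reading of the sentence. No other part of the protocol corrects it.

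That the bias equals the difference in means whatever the correlation is algebra and needs no assumption. The sizes do rest on assumptions: limits of ±13.1 to ±5.9 points and a difference-mean correlation of -0.60 to -1.00 for SDs of 3 and 6, and a bias of 30 to 67 points for the assumed means. Other values would change the numbers but not the conclusion that the plot cannot inform the CT validation.

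Severity is moderate. The analysis is wrongly specified and could mislead in a report, but it is descriptive, carries no decision rule, and sits beside an appropriate analysis of the same pair. The 3He versus 129Xe VDP plot is valid and should stay.

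**What to change.** Amend one sentence in Section 8:

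- Delete WA% from the Bland-Altman sentence.
- Restrict Bland-Altman to 3He VDP versus 129Xe VDP, in participants imaged with both gases at the same session and under the same condition. This needs stating because the protocol allows either gas or both, and because Visit 1 includes imaging before and after methacholine.
- State that WA% versus 129Xe VDP is assessed as an association only, by the Pearson correlation with 95% CI already planned in that paragraph.

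The cost is a wording change. No additional data, visits, scans or participants are needed.
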